6.3 Risks and Benefits

Potential risks

The potential risks to participants in this trial include risks associated with:

1. Venepuncture and intravenous cannulation

Localised bruising and discomfort can occur at the site of venepuncture. Infrequently fainting may occur. The total volume of blood drawn over a six month period will be 356mL, which should not compromise the health of these healthy individuals.

An intravenous cannula is routinely inserted into a peripheral (usually forearm) vein prior to bronchoscopy to administer intravenous sedation and removed once the procedure is completed. The risks of cannulation are identical to those associated with venepuncture. Additionally cannulation carries a small risk of soft tissue infection which will be minimised by an aseptic insertion technique and is easily recognisable and treatable. The short duration of cannulation (a few hours) further minimises this risk.

2. Vaccination

MVA85A has undergone thorough pre-clinical testing and has now been administered to over 2500 healthy human individuals with one possible SAR. The potential known adverse events associated with vaccination are:

Local reaction from aerosol inhaled vaccination

Expected reactions to inhaled vaccination include mild throat discomfort and coughing. Transient bronchospasm (causing wheeze) is possible. In the completed aerosolised trials (TB026 and TB035) there was no significant difference between respiratory adverse events or pulmonary function tests between the group receiving a priming immunisation with aerosol MVA85A and the group receiving a priming immunisation with ID MVA85A. In both groups AEs were infrequent and mild. In TB035, of the 9 subjects who received an aerosol boost vaccination 1 month after ID prime, 7 experienced transient mild to moderate respiratory AEs. All were self-limiting. This only occurred in subjects receiving an aerosol boost 1 month after an ID prime. The last 3 subjects in this group did not therefore receive an aerosol MVA85A boost.

Systemic reactions

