11.2 Definitions

Adverse Event (AE)

An AE is any untoward medical occurrence in a volunteer, which may occur during or after administration of an Investigational Medicinal Product (IMP) and does not necessarily have a causal relationship with the intervention. An AE can therefore be any unfavourable and unintended sign (including an abnormal laboratory finding), symptom or disease temporally associated with the study intervention, whether or not considered related to the study intervention.

Each adverse event will be graded by the participant according to the table for grading severity of adverse events (see Section 11.7). Severity gradings may be reviewed and discussed with the participants at the clinic visits.

Adverse Reaction (AR)

An AR is any untoward or unintended response to an IMP. This means that a causal relationship between the IMP and an AE is at least a reasonable possibility, i.e., the relationship cannot be ruled out. All cases judged by the reporting medical Investigator as having a reasonable suspected causal relationship to an IMP (i.e. possibly, probably or definitely related to an IMP) will qualify as adverse reactions.

Unexpected Adverse Reaction

An adverse reaction, the nature or severity of which is not consistent with the applicable product information (e.g., IB for an unapproved IMP).

Serious Adverse Event (SAE)

An SAE is an AE that results in any of the following outcomes, whether or not considered related to the study intervention.

- Death.
- Life-threatening event (i.e., the volunteer was, in the view of the Investigator, at immediate risk of death from the event that occurred). This does not include an AE that, if it occurred in a more severe form, might have caused death.

- Persistent or significant disability or incapacity (i.e., substantial disruption of one's ability to carry out normal life functions).
- Hospitalisation or prolongation of existing hospitalisation, regardless of length of stay, even if it is a precautionary measure for continued observation. Hospitalisation (including inpatient or outpatient hospitalisation for an elective procedure) for a pre-existing condition that has not worsened unexpectedly does not constitute a serious AE.

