- An important medical event (that may not cause death, be life threatening, or require hospitalisation) that may, based upon appropriate medical judgment, jeopardise the volunteer and/or require medical or surgical intervention to prevent one of the outcomes listed above. Examples of such medical events include allergic reaction requiring intensive treatment in an emergency room or clinic, blood dyscrasias, or convulsions that do not result in inpatient hospitalisation.
- Congenital anomaly or birth defect.

Serious Adverse Reaction (SAR)

An adverse event (expected or unexpected) that is both serious and, in the opinion of the reporting Investigator or Sponsors, believed to be possibly, probably or definitely due to an IMP or any other study treatments, based on the information provided.

Suspected Unexpected Serious Adverse Reaction (SUSAR)

A serious adverse reaction, the nature and severity of which is not consistent with the information about the medicinal product in question set out in the IB or SmPC.

NB: To avoid confusion or misunderstanding the following note of clarification is provided: "Severe" is often used to describe intensity of a specific event, which may be of relatively minor medical significance. "Seriousness" is the regulatory definition supplied above.

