11.3 Foreseeable Adverse Reactions

Foreseeable adverse reactions are listed in section 6.3.

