11.4 Expected Serious Adverse Events

No serious adverse events are expected in this study.

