11.6 Reporting Procedures for All Adverse Events

All AEs occurring in the 14 days following each vaccination observed by the Investigator or reported by the volunteer, whether or not attributed to study medication, will be recorded on electronic diary cards. Data from the diary cards will be extracted at each safety review and following the last volunteer last visit (LVLV). Outside the diary card periods, expected local and systemic AEs (listed in table 7 below) will be specifically solicited at each visit, and graded by severity and causality (as detailed in sections 11.7 and 11.5). All AEs starting after the diary card period, or persisting after this period, will be recorded in the AE line listing of the CRF.

The overall appearance of the lung mucosa will be assessed at the day 7 bronchoscopy.

Any radiological changes to the lungs will be assessed at the day 28 CT thorax.

All AEs that result in a volunteer's withdrawal from the study will be followed up until a satisfactory resolution occurs, or until a non-study related causality is assigned (if the volunteer consents to this). Serious adverse events (SAEs) will be collected throughout the entire trial period.

Reporting Procedures for Serious AEs (see Safety Reporting SOP)

In order to comply with current regulations on serious adverse event reporting to regulatory authorities, the event will be documented accurately and notification deadlines respected. SAEs will be reported on the SAE forms to members of the study team immediately the Investigators become aware of their occurrence, as described in the site-specific SOP. Copies of all reports will be forwarded for review to the Chief Investigator and Principal Investigators (as the Sponsor's representatives) within 24 hours of the Investigator being aware of the suspected SAE. The local safety committee (LSC) will be notified of SAEs which are deemed possibly, probably or definitely related to study interventions; the LSC will be notified immediately (within 24 hours) of the Investigators' being aware of their occurrence. SAEs will not normally be reported immediately to the ethical committee(s) unless there is a clinically important increase in occurrence rate, an unexpected outcome, or a new event

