that is likely to affect safety of trial volunteers, at the discretion of the Chief Investigator and/or LSC. In addition to the expedited reporting above, the Investigator shall include all SAEs in the annual Development Safety Update Report (DSUR) report.

Reporting Procedures for SUSARS

The Chief Investigator will report all SUSARs to the MHRA and ethical committee(s) within required timelines (15 days for all SUSARs, unless life threatening in which case 7 days, with a final report within a further 8 days (total 15)). The Chief Investigator will also inform all Investigators concerned of relevant information about SUSARs that could adversely affect the safety of participants.

All SUSARs and deaths occurring during the study will be reported to the Sponsor. For all deaths, available autopsy reports and relevant medical reports will be made available for reporting to the relevant authorities.

Development Safety Update Report

A Development Safety Update Report (DSUR) will be submitted by the Sponsor to the competent authority and ethical committee on the anniversary of the first approval date from the regulatory authority for each IMP.

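### Section 11.2 links nature and severity by 'and' for a SUSAR but by 'or' for an unexpected reaction, so a serious reaction unexpected in one respect only could miss the timed regulatory report

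*Combined protocol and SAP*

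**What the plan says.** Section 11.2 (Definitions) contains two rules for unexpectedness, both in current text.

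- Unexpected Adverse Reaction: "An adverse reaction, the nature or severity of which is not consistent with the applicable product information", with the IB given as the example for an unapproved product.
- SUSAR: "A serious adverse reaction, the nature and severity of which is not consistent with the information about the medicinal product", with the IB or SmPC as the reference.

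Two short sections also bear on what is expected. Section 11.3 says "Foreseeable adverse reactions are listed in section 6.3". Section 11.4 says "No serious adverse events are expected in this study".

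For the inhaled route, section 6.3 lists reactions with a limited severity attached: "Expected reactions to inhaled vaccination include mild throat discomfort and coughing", and "Transient bronchospasm (causing wheeze) is possible".

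The SUSAR label decides the external report. Section 11.6 says "The Chief Investigator will report all SUSARs to the MHRA and ethical committee(s) within required timelines": 15 days in general, or 7 days if life-threatening with the final report up to 8 days later (7 + 8 = 15). It also has the Chief Investigator pass relevant SUSAR information to all investigators concerned.

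**The concern.** One section gives two tests for the same idea, and they differ in the connecting word. With *or*, a departure in either respect is enough. With *and*, read literally, both are needed.

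The difference matters where a listed kind of reaction occurs in a worse form than listed. Take bronchospasm after inhalation that leads to a hospital stay, which section 11.2 counts as serious even when the stay is precautionary. If the reference document lists bronchospasm only as a transient event, the severity is new and the nature is not. The event is unexpected under one definition and falls outside the other.

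What is at stake is the timed report to the MHRA and the ethics committee, and the SUSAR notice to investigators. The primary objective is safety, and section 6.2 describes this as the first aerosol use of MVA85A in people with latent *M.tb* infection. The trigger for external reporting should therefore not depend on which of two adjacent definitions is applied.

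**Working it through.** No arithmetic on trial data applies, and the plan gives no figure to reproduce. The check sets the rules side by side.

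**Inputs.** The two definitions in section 11.2; the expectedness statements in 11.3 and 11.4; the reporting duties in 11.6 and 11.9.

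**Step 1: the two rules.** Take a reaction already judged serious and related. Let N mean that its nature is not consistent with the reference document, and S that its severity is not consistent.

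- Unexpected Adverse Reaction = N or S.
- SUSAR, read literally = N and S.

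| N | S | Unexpected (N or S) | SUSAR, literal (N and S) | Agree? |
|---|---|---|---|---|
| yes | yes | yes | yes | yes |
| no | yes | yes | no | **no** |
| yes | no | yes | no | **no** |
| no | no | no | no | yes |

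The *or* rule captures 3 of 4 combinations and the literal *and* rule captures 1 of 4, so they disagree in 3 − 1 = 2. These are counts of logical cases, not probabilities. The documents give no basis for saying how often each would arise.

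**Step 2: locate the example.** A serious, more severe form of a reaction whose nature is already listed is the second row (N no, S yes).

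**Step 3: who is told if the event is not classed as a SUSAR.**

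| Recipient | Route in the protocol | Depends on the SUSAR label? |
|---|---|---|
| Chief and Principal Investigators | All SAE reports, within 24 hours (11.6) | No |
| Local Safety Committee | Related SAEs, within 24 hours (11.6, 11.9) | No |
| Ethics committee | Not immediate by default; exceptions at the discretion of the Chief Investigator and/or LSC (11.6). Notified under local procedures (16.3) | The 7/15-day report does |
| MHRA | 7/15-day SUSAR report; otherwise the annual DSUR (11.6) | The 7/15-day report does |
| All investigators concerned | SUSAR information notice (11.6) | Yes |

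Apart from a provision on making reports of deaths available to authorities, the annual DSUR is the only route to the MHRA that section 11 states for a serious reaction not classed as a SUSAR.

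**Step 4: test whether 11.4 closes the gap.** If 11.4 governs expectedness, every serious related reaction is unexpected and all four combinations point to SUSAR handling. But the SUSAR definition refers to the IB or SmPC, not to 11.4. Section 11.4 also speaks of seriousness, while both definitions turn on nature and severity; the note at the end of section 11.2 separates seriousness from severity. So 11.4 points in the protective direction without being tied to the test. As drafted, the protocol supports three answers: 1, 3 or 4 of the 4 combinations.

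**The case against.** The strongest reply is that a sensible reader would not be misled. The U in SUSAR stands for a term that section 11.2 itself defines with *or*. The SUSAR phrase can even be read as met when either element is inconsistent. Section 11.4 declares no serious event expected. The 24-hour routes do not depend on expectedness: for related SAEs, "the LSC will be notified immediately (within 24 hours) of the Investigators' being aware of their occurrence". Section 11.6 calls these routes expedited, and in section 11.9 the committee's power to place the study on hold follows an intervention-related SAE, not a SUSAR.

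Most of this stands, and it limits the consequence. It does not remove the conflict: the protective reading requires one definition to override another, and none of the 24-hour routes names the MHRA.

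The bronchospasm example also has a limit. If the IB is the reference, section 6.3 is not, and the IB is not among the documents. If the IB does not list bronchospasm at all, nature and severity could both be inconsistent and even the *and* rule would be met. The example is therefore conditional on what the IB lists.

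Three stronger readings are tempting and are not supported:

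- **That such events would escape expedited reporting.** The documents show only that the timed MHRA and ethics report, and the SUSAR notice, could be missed on a literal reading. The internal 24-hour routes still operate.
- **That any severe form of a listed reaction is affected.** A severe but non-serious reaction is not a SUSAR under either wording.
- **That the TB035 experience, with respiratory events in 7 of 9 volunteers, measures the size of the problem.** Section 6.3 describes those events as mild to moderate, self-limiting, and confined to an aerosol boost one month after an intradermal prime. This trial gives a single vaccination and excludes earlier MVA85A recipients. Section 6.3 reports infrequent, mild events after aerosol priming, so the figure says nothing about serious reactions here.

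**Conclusion.** The inconsistency is real and lies in operative text. On the literal wording, a serious related reaction that is unexpected in nature only, or in severity only, meets the definition of an unexpected reaction but not that of a SUSAR. It could then miss the 7/15-day report to the MHRA and ethics committee and the SUSAR notice to investigators.

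The conclusion rests on two assumptions: that the *and* is applied literally, and, for the worked example, that the reference document lists the nature of the reaction but not its more serious form. The risk is moderated by section 11.4 and the 24-hour routes, so the event could be misclassified; the documents do not show that it would be.

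This is a drafting fault in a safety-reporting definition, with no effect on any estimate, comparison or sample size. It is worth correcting because safety is the primary objective and the correction is very small.

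**What to change.** 1. In the SUSAR definition in section 11.2, replace the *and* between nature and severity with *or*, so that it matches the Unexpected Adverse Reaction definition.
2. Name the same reference document in both definitions. One now cites the applicable product information, with the IB as an example; the other cites the IB or SmPC.
3. Cross-refer to section 11.4 in the SUSAR definition, and state whether its declaration that no serious events are expected governs expectedness. Say also whether the section 6.3 list, reached through 11.3, has any part in that judgement.

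The cost is one word and two short clarifying sentences. No change to data collection, visits, sample size or analysis follows.

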11.3 Foreseeable Adverse Reactions

Foreseeable adverse reactions are listed in section 6.3.

11.4 Expected Serious Adverse Events

No serious adverse events are expected in this study.

11.5 Causality Assessment

For every unsolicited AE, an assessment of the relationship of the event to the administration of the vaccine will be undertaken. An intervention-related AE refers to an AE for which there is a probable or definite relationship to administration of a vaccine. An interpretation of the causal relationship of the intervention to the AE in question will be made, based on the type of event, the relationship of the event to the time of vaccine administration and the known biology of the vaccine therapy (Table 5). Causality assessment will take place during interim analyses and at the final safety analysis.

Table 5. Guidelines for assessing the relationship of vaccine administration to an AE

0	No Relationship	No temporal relationship to trial product; and Alternate aetiology (clinical state, environment or other interventions); and Does not follow known pattern of response to vaccine
1	Unlikely	Unlikely temporal relationship to trial product; and Alternate aetiology likely (clinical state, environment or other interventions); and Does not follow known typical or plausible pattern of response to vaccine
2	Possible	Reasonable temporal relationship to trial product; or Event not readily produced by clinical state, environment or other interventions; or Similar pattern of response to that seen with other vaccines
3	Probable	Reasonable temporal relationship to trial product; and Event not readily produced by clinical state, environment or other interventions; and Known pattern of response seen with other vaccines
4	Definite	Reasonable temporal relationship to vaccine; and Event not readily produced by clinical state, environment or other interventions; and Known pattern of response seen with the vaccine

11.6 Reporting Procedures for All Adverse Events

All AEs occurring in the 14 days following each vaccination observed by the Investigator or reported by the volunteer, whether or not attributed to study medication, will be recorded on electronic diary cards. Data from the diary cards will be extracted at each safety review and following the last volunteer last visit (LVLV). Outside the diary card periods, expected local and systemic AEs (listed in table 7 below) will be specifically solicited at each visit, and graded by severity and causality (as detailed in sections 11.7 and 11.5). All AEs starting after the diary card period, or persisting after this period, will be recorded in the AE line listing of the CRF.

The overall appearance of the lung mucosa will be assessed at the day 7 bronchoscopy.

Any radiological changes to the lungs will be assessed at the day 28 CT thorax.

All AEs that result in a volunteer's withdrawal from the study will be followed up until a satisfactory resolution occurs, or until a non-study related causality is assigned (if the volunteer consents to this). Serious adverse events (SAEs) will be collected throughout the entire trial period.

Reporting Procedures for Serious AEs (see Safety Reporting SOP)

In order to comply with current regulations on serious adverse event reporting to regulatory authorities, the event will be documented accurately and notification deadlines respected. SAEs will be reported on the SAE forms to members of the study team immediately the Investigators become aware of their occurrence, as described in the site-specific SOP. Copies of all reports will be forwarded for review to the Chief Investigator and Principal Investigators (as the Sponsor's representatives) within 24 hours of the Investigator being aware of the suspected SAE. The local safety committee (LSC) will be notified of SAEs which are deemed possibly, probably or definitely related to study interventions; the LSC will be notified immediately (within 24 hours) of the Investigators' being aware of their occurrence. SAEs will not normally be reported immediately to the ethical committee(s) unless there is a clinically important increase in occurrence rate, an unexpected outcome, or a new event

that is likely to affect safety of trial volunteers, at the discretion of the Chief Investigator and/or LSC. In addition to the expedited reporting above, the Investigator shall include all SAEs in the annual Development Safety Update Report (DSUR) report.

Reporting Procedures for SUSARS

The Chief Investigator will report all SUSARs to the MHRA and ethical committee(s) within required timelines (15 days for all SUSARs, unless life threatening in which case 7 days, with a final report within a further 8 days (total 15)). The Chief Investigator will also inform all Investigators concerned of relevant information about SUSARs that could adversely affect the safety of participants.

All SUSARs and deaths occurring during the study will be reported to the Sponsor. For all deaths, available autopsy reports and relevant medical reports will be made available for reporting to the relevant authorities.

Development Safety Update Report

A Development Safety Update Report (DSUR) will be submitted by the Sponsor to the competent authority and ethical committee on the anniversary of the first approval date from the regulatory authority for each IMP.

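### Minor, cheap improvement: on-schedule bronchoscopy falls inside the 14-day AE diary and shares symptoms with the vaccine, but non-serious AEs are graded against the vaccine only, and sections 11.2 and 11.5 treat the grade Possible differently

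*Combined protocol and SAP*

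**What the plan says.** **Collection.** Section 11.6 records on the electronic diary "All AEs occurring in the 14 days following each vaccination observed by the Investigator or reported by the volunteer", regardless of attribution. Outside the diary period, expected events "will be specifically solicited at each visit, and graded by severity and causality (as detailed in sections 11.7 and 11.5").

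**Timing.** Table 1 (section 4.2) and section 9.6 put bronchoscopy at day 7, with a window of +4/-2 days. A Table 1 footnote anchors each visit to the actual date of the one before. Section 9.9 lets a postponed bronchoscopy be rescheduled within three weeks.

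**Shared symptoms.** Section 6.3 lists throat discomfort and influenza-like symptoms for the vaccine. It lists sore throat and flu-like symptoms for bronchoscopy.

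**Causality.** Section 11.5 requires an assessment against the vaccine for each unsolicited AE, using Table 5. It then states: "An intervention-related AE refers to an AE for which there is a probable or definite relationship to administration of a vaccine". Section 11.2 sets a different line for adverse reactions: events "possibly, probably or definitely related to an IMP) will qualify as adverse reactions".

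**Analysis.** Section 11 assesses safety by how often AEs occur and of what kind. Section 12 calls the endpoints descriptive and removes the comparator arm. Neither section plans a display that separates AEs before and after bronchoscopy.

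**The concern.** A volunteer who reports a sore throat or flu-like symptoms on the evening of bronchoscopy has two candidate causes, both named in section 6.3. No concurrent arm shows what the procedure produces alone. The protocol's one causality scale for non-serious AEs asks about the vaccine; bronchoscopy enters only under Table 5's general words about other interventions.

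Those words work at the top of the scale, where they keep procedure-related events out of Probable and Definite. At the bottom they are tied to a further condition that a shared symptom cannot meet. Such an event can therefore settle at Possible, where 11.2 and 11.5 disagree on what it counts as. At stake is how a few mild events are labelled in the safety account of a trial whose primary objective is safety.

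**Working it through.** The plan gives no figure to reproduce. Three checks apply.

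**1. Is bronchoscopy inside the diary?** Take vaccination as day 0 and the diary end as day 14. Days before bronchoscopy = its day number; days after = 14 minus that number.

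- Nominal: day 7 gives 7 before and 7 after.
- Window from day 7: 7 - 2 = 5 to 7 + 4 = 11. Before: 5 to 11. After: 14 - 11 = 3 to 14 - 5 = 9.
- Window from the actual previous visit (day 2 ±1, so days 1 to 3; the planned gap is 5 days): 1 + 5 - 2 = 4 to 3 + 5 + 4 = 12. Before: 4 to 12. After: 2 to 10.
- Postponed: if the three weeks run from day 7 (an assumption), up to 7 + 21 = day 28. Past day 14 the split is 14 and 0.

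An on-schedule procedure leaves at least 2 diary days, so the 1-2 day post-procedure flu-like symptoms described in 6.3 fall inside the diary.

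**2. Which Table 5 grades can a shared symptom reach?** Suppose bronchoscopy is the evident cause, and the symptom is of a type the vaccine is known to produce. Read pattern as type of symptom, since timing has its own clause.

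| Grade | Clauses joined by | Deciding clause | Result |
|---|---|---|---|
| 0 No relationship | and | "Alternate aetiology (clinical state, environment or other interventions); and Does not follow known pattern of response to vaccine" | Fails: matches the vaccine pattern |
| 1 Unlikely | and | "Alternate aetiology likely (clinical state, environment or other interventions); and Does not follow known typical or plausible pattern of response to vaccine" | Fails: same reason |
| 2 Possible | or | Reasonable timing, or "Event not readily produced by clinical state, environment or other interventions; or Similar pattern of response to that seen with other vaccines" | One clause is enough |
| 3 Probable | and | Not readily produced by another intervention | Fails: bronchoscopy produces it |
| 4 Definite | and | "Event not readily produced by clinical state, environment or other interventions; and Known pattern of response seen with the vaccine" | Fails: same reason |

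- Flu-like symptom: 6.3 says such symptoms can follow any vaccination, so the clause on other vaccines is met. The result is Possible whether timing is judged reasonable, unlikely or absent.
- Throat symptom: Possible if timing is judged reasonable. If it is not, and other vaccines do not cause the symptom, no grade is met.

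**3. What does Possible then mean?** Under 11.2 it is an adverse reaction. Under 11.5 it is not intervention-related, because that term starts at Probable.

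**Size per event.** One reclassified volunteer moves the proportion with an adverse reaction by 1/3 = 33.3 points in the Starter Group, and by 1/6 = 16.7 to 1/3 = 33.3 points in Group A (n = 6 to 3). This is simply 1/n; it does not say how often it happens.

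**The case against.** Several counter-arguments have force.

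- **Table 5 may not govern these events.** 11.5 requires causality for unsolicited AEs, and 11.6 requires it for expected events outside the diary. Throat and flu-like symptoms are foreseeable reactions and may be solicited. No section clearly applies Table 5 to solicited symptoms inside the diary. Table 7, which 11.6 cites as listing the expected events, contains severity grades only. This stands: the grading result is conditional, and the unclear scope is itself part of the point.
- **Table 5 offers guidelines.** 11.5 calls for interpretation from event type, timing and known biology. Vaccine flu-like symptoms are said to last 2-3 days, so an assessor could call a day 7 onset off-pattern and reach Unlikely. This also stands. However, if only the clause on this vaccine is read that way, a flu-like symptom meets both Unlikely and Possible.
- **Serious events are covered more widely.** The SAR definition in 11.2 includes other study treatments, and committee notification in 11.6 covers study interventions. The point is therefore limited to non-serious AEs.
- **The 11.2/11.5 difference exists without bronchoscopy.** They are two separately defined terms. True, but a shared symptom held at Possible falls exactly between them.
- **Much can be rebuilt later.** The bronchoscopy report is a source document (13.1), so a before/after listing is possible if onset dates are kept. A contemporaneous attribution is harder to recover.

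Two stronger readings are tempting. A reader might infer that nothing in the trial records which cause was judged; the CRF, diary layout and safety SOP are not in the documents, so this cannot be said. A reader might also infer that a vaccine reaction at the day 7 T-cell peak (9.6) would be blamed on the procedure; no section links that peak in blood to symptoms.

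**Conclusion.** The point holds as a minor reporting improvement. The overlap in time and symptoms is certain for an on-schedule bronchoscopy. The confinement to Possible rests on two assumptions: that Table 5 is applied to the event, and that pattern means type of symptom. For throat symptoms it also needs timing to be judged reasonable.

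The expected size is unknown, because the documents give no symptom rate after bronchoscopy. It is probably small: 6.1 reports that bronchoscopies were well tolerated in TB026, and 6.3 describes AEs after a first dose in the earlier aerosol trials as infrequent and mild. Total AE counts are the same however events are attributed, and sections 11 and 12 specify no adverse-reaction table.

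A reader might infer that dose escalation or stopping could be distorted. The documents do not support that: neither 9.11 nor 11.1 uses an AE frequency threshold. The trial's validity is not in question.

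**What to change.** In sections 11.5, 11.6 and 12:

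1. Keep the full 14-day AE table as the main display. Add a descriptive breakdown of the same AEs by onset before or after the actual start of bronchoscopy, with each volunteer's days at risk in each segment.
2. For all AEs, solicited and unsolicited, inside and outside the diary period, record relatedness to the vaccine and, separately, to bronchoscopy or sedation.
3. Reconcile 11.2 and 11.5 on the status of Possible. State how Table 5 applies when another intervention is the evident cause of a symptom that the vaccine can also produce.

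The cost is one attribution field and the bronchoscopy start time, where the CRF does not already hold them, plus one table. No visit or test is added. The downside is that the segments differ in length between volunteers, and a late bronchoscopy may leave no diary days after it. The breakdown is therefore descriptive only and must be read with the days at risk.
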